6.10.2. Follow-up Contact (Day 57 (+3 days) End of Study)

Follow-up contact will be completed 28 +3 calendar days after the last administration of the investigational product to capture any adverse events including ongoing potential hypersensitivity and/or application site reactions and to review and record concomitant medications (see the [Time Period for Collecting AE/SAE Information](#) section). Contact with the subject may be done via a phone call. Any subject with a new or ongoing adverse event at the time of the Day 57 visit should however be seen in the clinic for evaluation of that adverse event.

CCI [Redacted]

[Redacted]

| [Redacted]

| [Redacted]

| [Redacted]

| [Redacted]

| [Redacted]

| [Redacted]

| [Redacted]

| [Redacted]

CCI [Redacted]

| [Redacted]

| [Redacted]

| [Redacted]

| [Redacted]

CC
I [REDACTED]

I [REDACTED]

I [REDACTED]

I [REDACTED]

I [REDACTED]

[REDACTED]

I [REDACTED]

I [REDACTED]

CC
I [REDACTED]

CC
I [REDACTED] CCI

I [REDACTED]

I [REDACTED]

CC [REDACTED]

6.12. Subject Withdrawal/Early Termination

The following criteria will be considered for the subjects' discontinuation or withdrawal from the study:

- The occurrence of adverse events that require the subject to stop participation in the study, due to availability for, or intolerance to, the study procedures.
- Adverse effects of the study active ingredient that are considered to be clinically significant by the physician in charge, and/or might be harmful to the subjects' health.
- Abnormal laboratory tests considered to be clinically relevant.
- Concurrent diseases that require use of a prohibited medication.
- CCI [REDACTED]
- Clinically significant hypersensitivity reactions.

Subjects may be withdrawn from the study at any time at their parent(s)/legal guardian's request, or they may be withdrawn at any time at the discretion of the investigator or sponsor for safety (see also the [Withdrawal From the Study Due to Adverse Events](#) section) or, behavioral reasons, or the inability of the subject's parent(s)/legal guardian to comply with the protocol required schedule of study visits or procedures at a given investigator site. The early termination visit applies only to subjects who are enrolled and then are prematurely withdrawn from the study.

Subjects should return to the clinic for the early termination visit as early as practically feasible following the decision to withdraw from the study. Subject's parent(s)/legal guardian should be questioned regarding their reason for withdrawal. Every effort must be made to complete the assessments outlined in the Day 29/End of Treatment visit ([Section 6.8](#)). Subjects will in addition be requested to be available for the follow-up contacts at 1 week and 4 weeks after last dose of study treatment.

Lack of completion of all or any of the withdrawal/early termination procedures will not be viewed as protocol deviations so long as the subject's safety was preserved.

Withdrawal of consent:

Subjects for whom it has been requested to discontinue receipt of study treatment by the parent(s)/legal guardian must continue to be followed for protocol specified follow-up procedures. The only exception to this is when a subject's parent(s)/legal guardian specifically withdraws consent for the subject for any further contact with him or her or persons previously authorized to provide this information. The subject's parent(s)/legal

guardian should notify the investigator in writing of the decision to withdraw consent from future follow-up, whenever possible. The withdrawal of consent should be explained in detail in the medical records by the investigator, as to whether the withdrawal is only from further receipt of investigational product or also from study procedures and/or post-treatment study follow-up, and entered on the appropriate case report form (CRF) page. In the event that vital status (whether the subject is alive or dead) is being measured, publicly available information should be used to determine vital status only as appropriately directed in accordance with local law.

Subjects who are withdrawn from the study may be replaced at the discretion of the investigator upon consultation with the sponsor. In the [REDACTED] cohort, subjects discontinuing for reasons other than TEAE may be replaced at the discretion of the sponsor to ensure 16 subjects complete the [REDACTED] assessments.

Lost to follow-up:

All reasonable efforts must be made to locate subjects to determine and report their ongoing status. This includes follow-up with persons authorized by the subject's parent(s)/legal guardian as noted above. Lost to follow-up is defined by the inability to reach the subject's parent(s)/legal guardian after a minimum of 2 documented phone calls, faxes, or e-mails as well as lack of response by the subject to 1 registered mail letter. All attempts should be documented in the subject's medical records. If it is determined that the subject has died, the site will use locally permissible methods to obtain the date and cause of death. If the investigator's use of a third-party representative to assist in the follow-up portion of the study has been included in the subject's informed consent, then the investigator may use a sponsor-retained third-party representative to assist site staff with obtaining the subject's parent(s)/legal guardian contact information or other public vital status data necessary to complete the follow-up portion of the study. The site staff and representative will consult publicly available sources, such as public health registries and databases, in order to obtain updated contact information. If, after all attempts, the subject remains lost to follow-up, then the last-known-alive date as determined by the investigator should be reported and documented in the subject's medical records.

If a subject is not brought back for a scheduled visit, every effort should be made to contact the subject's parent(s)/legal guardian. The Investigator or site staff should attempt to contact the subject's parent(s)/legal guardian twice. After 2 attempts, CRU staff may send a registered letter. If no response is received from the subject's parent(s)/legal guardian, the subject will be considered lost to follow up. All attempts to contact the subject's parent(s)/legal guardian and information received during contact attempts must be documented in the subject's medical record. In any circumstance, every effort should be made to document subject outcome, if possible. The investigator should inquire about the reason for withdrawal, request the subject to return for a final visit, if applicable, and follow-up with the subject's parent(s)/legal guardian regarding any unresolved adverse events (AEs).

7. ASSESSMENTS

Every effort should be made to ensure that the protocol-required tests and procedures are completed as described. However, it is anticipated that from time to time there may be circumstances outside of the control of the investigator that may make it unfeasible to perform the test. In these cases the investigator will take all steps necessary to ensure the safety and well-being of the subject. When a protocol-required test cannot be performed, the investigator will document the reason for this and any corrective and preventive actions that he or she has taken to ensure that normal processes are adhered to as soon as possible. The study team will be informed of these incidents in a timely manner.

For samples being collected and shipped, detailed collection, processing, storage, and shipment instructions and contact information will be provided to the investigator site prior to initiation of the study.

7.1. Safety

7.1.1. Clinical Laboratory Evaluations

The following safety laboratory tests will be performed at times defined in the [STUDY PROCEDURES](#) section of this protocol. Additional laboratory results may be reported on these samples as a result of the method of analysis or the type of analyzer used by the clinical laboratory; or as derived from calculated values. These additional tests would not require additional collection of blood. Unscheduled clinical laboratory assessments may be obtained at any time during the study to assess any perceived safety concerns.

The clinical laboratory test parameters that will be reviewed for safety evaluation are presented in [Table 2](#).

Table 2. Clinical Laboratory Test Parameters

| Hematology | Chemistry | Other Bioanalytical Laboratory Assessment |
|------------------------|----------------------------|---|
| Hemoglobin | Blood urea nitrogen | CCI [REDACTED] |
| Hematocrit | Glucose (non-fasting) | [REDACTED] |
| Red blood cell count | Creatinine | |
| Platelet count | Sodium | |
| White blood cell count | Potassium | |
| (% and absolute) | Chloride | |
| • Neutrophils | Bicarbonate | |
| • Eosinophils | Alanine aminotransferase | |
| • Monocytes | Aspartate aminotransferase | |
| • Basophils | Total bilirubin | |
| • Lymphocytes | Alkaline phosphatase | |
| | Albumin | |
| | Total protein | |
| | Lactate | |
| | Calculation of osmolal gap | |
| | Calculation of anion gap | |

Baseline clinical laboratory tests will be drawn during the Screening visit, after assessment of vital signs and prior to the first investigational product application.

At the discretion of the Investigator, a lidocaine-based topical anesthetic (eg, lidocaine 4% cream) may be used prior to clinical laboratory sample collection to decrease potential discomfort to the subject provided the anesthetic CCI [REDACTED]. The skin must be thoroughly cleansed prior to blood sample collection.

The Investigator will review all clinical laboratory test results for safety evaluation upon receipt. After reviewing the laboratory reports and evaluating the results for clinical significance, the Investigator or designee must sign and date the laboratory report. Clinically significant laboratory abnormalities are defined as abnormal values that have clinical manifestations or require medical intervention. Clinically significant laboratory abnormalities noted from the Screening Visit will be recorded in the medical history. Note: Upon receipt of the Screening serum chemistry, and hematology results, if there are any clinically significant abnormalities that the PI or designee considers prohibit initiation of investigational product treatment, the PI or designee may contact the sponsor medical monitor to discuss the appropriate course of action.

A clinically significant laboratory abnormality detected after the Screening Visit may reflect the development of an AE. Whenever possible, Investigators should report the clinical diagnosis suggested by the laboratory abnormality rather than listing individual abnormal test results as AEs. If no diagnosis has been found to explain the abnormal laboratory result, the clinically significant lab result should be recorded as an AE, reflecting the lack of a diagnosis (see [Section 8.2.2](#)).

7.1.2. Physical Examination, including Height/Length, and Weight

Physical examinations, including height/length, and weight will be performed at times specified in the [STUDY PROCEDURES](#) section of this protocol.

Physical examinations may be conducted by a physician, trained physician's assistant, or nurse practitioner as acceptable according to local regulation. A full physical examination will include, but is not limited to the following organ or body systems: head, ears, eyes, nose, mouth, skin, heart and lung examinations, lymph nodes, gastrointestinal, musculoskeletal, abdomen (liver, spleen), cardiovascular, and neurological systems. In addition, an assessment will be made of the condition of all AD-involved skin.

The limited or abbreviated physical examination will be focused on general appearance, the respiratory, cardiovascular, and neurological systems, as well as towards symptoms reported by the subject's parent(s)/legal guardian. In addition, symptoms and signs of diarrhea and vomiting should be assessed to monitor for evidence of dehydration.

The neurological examination component of all physical examinations should include evaluation of clinical signs that have been associated, in published reports, with  toxicity²¹ including central nervous system depression, seizure activity, ataxia, as well as somnolence, poor feeding and irritability which are considered newly emergent and independent of the subject's AD related signs.

Results from blood pressure and prior ECG assessments should be referred to when performing the cardiovascular component of all physical examinations in order to actively monitor for clinical signs that have been associated, in published reports, with  toxicity including hypotension and cardiac arrhythmia.

For both weight and height/length measurements, the investigator or examiner should be trained in measuring height/length and weight as well as in calibration procedures. Ideally, the same person should measure the subject at every visit. Attempts should be made to schedule visits, so that measurements can be taken at approximately the same time throughout the study. The parent / caregiver is needed to help with measurement and to soothe and comfort the child. Explain to the parent/ caregiver the steps in the procedures and that it is important to keep the child still and calm to obtain good measurements.

For measuring weight, a scale with appropriate range and resolution is used and must be placed on a stable, flat surface. Subjects must remove shoes, bulky layers of clothing, and jackets so that only light clothing remains. They must also remove the contents of their pockets and remain still during measurement of weight.

For measuring length, a length board (infantometer) must be used and be placed on a flat, stable surface, such as a table.

For both weight and height/length, three reproducible measurements of both the child's weight and height/length should be recorded and the average of the 3 recordings will be entered onto the eCRF.

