4.1. Inclusion Criteria

Subjects must meet all of the following inclusion criteria to be eligible for enrollment into the study:

1. Is male or female aged at least 3 months at the Screening visit to less than 24 months on Baseline/Day 1.
2. Has a clinical diagnosis of AD according to the criteria of Hanifin and Rajka (1980) (See [Appendix 2](#)).

[REDACTED]

[REDACTED]

- b. [REDACTED]

[REDACTED]

[REDACTED]

[REDACTED]

5. Evidence of a personally signed and dated informed consent document indicating that the subject's parent(s)/legal guardian has been informed of all pertinent aspects of the study.
6. Parent(s)/legal guardian who is/are willing and able to comply with all scheduled visits, treatment plan, laboratory tests and other study procedures.

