6.1.5. Height/Length and Weight

Height/length and weight values and change from baseline at Day 29/Early Termination and clinical significant change will be summarized according to Pfizer standards.

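### The weighing rule leaves infants in light clothing and fixes neither diaper state nor clothing between visits, so avoidable error enters each child's weight change and the judgement of whether it is clinically significant

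*Protocol*

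**What the plan says.** Protocol Section 4.1 sets the age range: "Is male or female aged at least 3 months at the Screening visit to less than 24 months on Baseline/Day 1". Protocol Section 2 and SAP Section 3.1 make weight one of the measures for which the incidence of clinically significant change is a primary endpoint. The Schedule of Activities has weight taken at Screening, Baseline/Day 1 and Day 29/Early Termination.

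Protocol Section 7.1.2 gives the clothing rule: "Subjects must remove shoes, bulky layers of clothing, and jackets so that only light clothing remains". It continues: "They must also remove the contents of their pockets and remain still during measurement of weight". The equipment rule is "a scale with appropriate range and resolution is used and must be placed on a stable, flat surface", with no resolution in grams.

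The same section sets several controls:
- Examiners are to be trained in measurement and calibration.
- "Ideally, the same person should measure the subject at every visit".
- Visits should be arranged so that "measurements can be taken at approximately the same time throughout the study".
- Three reproducible readings are taken, and "the average of the 3 recordings will be entered onto the eCRF".

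SAP Section 6.1.5 summarises "Height/length and weight values and change from baseline at Day 29/Early Termination", together with clinically significant change, by reference to sponsor standards. SAP Section 3.3 defines baseline as the last evaluation before the first dose.

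Neither document says whether the diaper is on, off, fresh or tared at weighing, and neither requires the same clothing from one visit to the next.

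**The concern.** The quantity of interest is the difference between two weighings about 28 days apart in a small, growing child. Anything worn at one visit and not at the other goes straight into that difference. Light clothing is a category and not a fixed weight, and a diaper may be dry or wet.

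Weight enters the primary endpoint through a judgement on each child, so error in the individual change is what matters. It could mask poor gain in one child or suggest a loss in another. Two features of the plan leave that judgement exposed. There is no control arm in which the same artefact would appear, and the visible text gives no numeric criterion for a clinically significant weight change.

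**Working it through.** **The plan's own figure.** The only design figure that can be recomputed is the sample size in Protocol Section 9.1: 100 completers with 20% dropout gives 100 / (1 − 0.20) = 125, which matches. It was not based on power and does not bear on this point. The documents give no figure for clothing weight, diaper weight or expected gain.

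**Model.** Let c be the visit-to-visit SD of one child's clothing plus diaper weight, independent between visits. Let s be the SD of a single scale reading, and k the number of readings averaged at each visit. The error SD of the change between two visits is

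SD(change) = sqrt(2 × (s²/k + c²)).

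**Inputs.** k = 3 is from Protocol Section 7.1.2. c = 0.05 to 0.20 kg and s = 20 g are assumptions.

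**Step 1: clothing and diaper error alone.**
- c = 0.05 kg: sqrt(2) × 0.05 = 0.07 kg
- c = 0.20 kg: sqrt(2) × 0.20 = 0.28 kg

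**Step 2: does averaging three readings help?** With s = 20 g:

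| c (g) | SD of change, one reading (g) | SD of change, mean of three (g) |
|---|---|---|
| 50 | 76.2 | 72.6 |
| 100 | 144.2 | 142.4 |
| 150 | 214.0 | 212.8 |

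Averaging divides s² by 3 and leaves c² untouched. At c = 100 g the SD falls by less than 2 g.

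**Step 3: group mean.** With 100 completers and random clothing differences, the standard error that this contributes to the mean change is SD(change)/sqrt(100):
- c = 50 g: 7.3 g
- c = 100 g: 14.2 g
- c = 150 g: 21.3 g
- c = 200 g: sqrt(2 × (400/3 + 40,000)) / 10 = 28.3 g

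**Step 4: individual classification.** The chance that a child is misclassified depends on the distance between the true change and the threshold, divided by SD(change). No threshold is visible in either document, so this step cannot be completed.

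**The case against.** The strongest defence is that Section 7.1.2 already sets a common state for every weighing. Shoes, jackets and bulky layers are off, examiners are trained, and the same person and a similar time of day are preferred. Two pre-treatment weights, at Screening and Baseline/Day 1, could expose an odd reading. The Day 29 weight comes with a full physical examination and adverse event review, and poor feeding is among the signs that examiners are asked to evaluate. The SAP states no hypothesis, and the change from baseline is a descriptive summary.

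Much of this stands. The group summary is barely affected if clothing differences are random, and the scale reading is not the only evidence on a child. The instruction on shoes and pockets fits a young infant oddly but causes no error, and older children in the age range may well wear shoes.

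What does not stand is the idea that these controls deal with clothing and diaper. Training, examiner and time of day do not fix what the child wears, and Step 2 shows that repeat readings do not either. A second pre-treatment weight may flag an odd baseline, but Day 29 has only one weighing visit.

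A reader might go further and infer that clothing differences can be as large as the four-week weight gain. The documents do not support that, since they give neither quantity. If the true gain is assumed to be 0.2 to 0.5 kg, the four corners of the assumed range are:
- 0.07/0.5 = 14%
- 0.07/0.2 = 35%
- 0.28/0.5 = 57%
- 0.28/0.2 = 140%

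Only the pairing of the largest error with the smallest gain exceeds 100%. That error implies 95% of between-visit differences within about ±0.55 kg (1.96 × 0.28), which is hard to square with light clothing. Mean gain is also the wrong yardstick, because the endpoint is the incidence of clinically significant change and not the average change.

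**Conclusion.** The point holds as a minor improvement. The stated weighing method lets avoidable error into each child's weight change, and so into the individual judgement behind one component of the primary endpoint. The existing controls do not remove it.

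Its size rests on assumption. For a visit-to-visit SD of 0.05 to 0.20 kg, the error SD of the change is about 0.07 to 0.28 kg. The effect on classification cannot be quantified without a threshold. The contribution to the standard error of the group mean is about 7 to 28 g with 100 completers. That figure holds only if clothing differences are random: a consistent shift in clothing or diaper state between Baseline/Day 1 and Day 29 would bias the mean and would not average out. Nothing here affects the sample size or calls the study's safety conclusions as a whole into question.

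**What to change.** In Protocol Section 7.1.2, replace the two clothing sentences with: *Weigh the child unclothed or in a clean dry diaper only, in the same state at Screening, Baseline/Day 1 and Day 29/Early Termination, on the same scale where possible.* Keep the requirement for the child to be still and the three-reading average.

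The cost is about a minute more per weighing and brief site training. Much of the undressing is likely to be needed anyway: ointment is applied to all treatable lesions at Baseline/Day 1, and the full examinations at Screening and Day 29 include the condition of all affected skin. If enrolment has already begun, apply the new rule only to children not yet weighed at Baseline/Day 1. Changing it between one child's two weighings would create the very difference it is meant to prevent.

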7.1.3. Electrocardiogram

A single standard supine 12-lead ECG will be performed at times defined in the [STUDY PROCEDURES](#) section of this protocol. In the event of a 12-lead ECG cannot be obtained due to technical reasons (eg, pediatric patient with small chest), a 6-lead ECG should be obtained instead. Assessment should be performed after the subject has been resting quietly and precede measurement of vital signs and blood draws whenever possible. An ECG collection device will be provided by a central vendor and ECG data will be submitted to the central laboratory for measurement. ECG interpretation will be provided directly to the site indicating central reader assessed relevance of abnormal findings. It is the responsibility of the investigator to assess the findings based on the subject's clinical presentation and determine clinical significance for a given subject. Any clinically significant changes from the Baseline/Day 1 ECG should be recorded as AEs and evaluated further as clinically warranted.

